#### **CLINICAL INVESTIGATION PLAN SYNOPSIS**

#### Study title

A prospective, multicenter study on Acuris™ - conometric concept for single tooth restoration. A 5-year follow-up study.

#### Study site(s) and number of subjects planned

Anticipated number of study sites 9 sites
Anticipated number of subjects/implants 157 subjects/157 implants

#### Study period

Anticipated First Subject In (FSI)

Anticipated Last Subject In (LSI)

Anticipated Last Subject Out (LSO)

Anticipated Last Subject Out (LSO)

Anticipated Data Base Lock (DBL)

2019 May

2020 August

2025 September

2026 February

#### Indication

The Conometric Abutments are intended to be used together with all implant brands of Dentsply Sirona Implants; Ankylos, Astra Tech Implant System or Xive, for fixed friction retained single crown restorations.

#### Investigational product

Conometric abutment, Conometric final cap.

#### Primary objective(s)

Prosthetic survival 1 year after permanent restoration.

#### Study design

A prospective, non-controlled, multicentre study on the Acuris-conometric concept.

#### Subject population

Subjects, aged between 18-75 years, in need of single tooth replacement.

#### Inclusion criteria

For inclusion in the study subjects must meet all of the following criteria:

- 1. Subject aged between 18-75 years
- 2. Subject signed and dated the informed consent form
- 3. In need of an implant replacing a missing tooth in position 17 to 27 or 37 to 47, and each subject can only receive one study implant.
- 4. Neighbouring tooth to the planned implant must have
  - a natural root or an implant supported restoration mesially
  - a natural root or an implant supported restoration distally

Exemption: If the planned implant is in the second molar position, an edentulous space is accepted distally.

- 5. Presence of natural tooth, partial prosthesis and/or implant supported restoration in the opposite jaw in contact with the planned crown
- 6. Deemed by the investigator as likely to present an initially stable implant situation

#### **Exclusion criteria**

Any of the following is regarded as a criterion for exclusion from the study (all criteria applies at study inclusion, but criteria numbered 1-5 also applies during the entire study period):

- 1. Unlikely to be able to comply with study procedures, according to Investigators judgement
- 2. Subject is not willing to participate in the study or not able to understand the content of the study
- 3. Unable or unwilling to return for follow-up visits for a period of five years
- 4. Involvement in the planning and conduct of the study
- 5. Simultaneous participation in another clinical study, or former participation in a clinical study during the last 6 months that may interfere with the present study
- 6. Previous enrolment in the present study
- 7. Severe non-compliance to CIP as judged by the Investigator and/or Dentsply Sirona Implants.
- 8. Uncontrolled pathological process in the oral cavity
- 9. Known or suspected current malignancy
- 10. History of radiation therapy in the head and neck region within 12 months prior to surgery
- 11. Systemic or local disease or condition that could compromise post-operative healing and/or osseointegration
- 12. Uncontrolled diabetes mellitus
- 13. Corticosteroids, iv bisphosphonates or any other medication that could influence postoperative healing and/or osseointegration
- 14. Current need for major bone grafting and/or augmentation in the planned implant area (minor grafting and soft tissue grafting are allowed)
- 15. Present alcohol and drug abuse
- 16. Smoking more than 10 cigarettes per day

#### **Exclusion criteria at Visit 5 (Permanent Restoration)**

17. Permanent restoration delivered later than 6 months after implant placement

### 1 Introduction

# 1.1 Background

Acuris is developed for a conometric mode of retention for fixed implant restorations, based on friction. The crown is fixed for the patient, but removable for the clinician. The components are developed based on the already marketed Ankylos SynCone System and accessories, incl. Ankylos Welding Cap for SynCone 5°, and is available for all implant brands from Dentsply Sirona Implants (Ankylos, Astra Tech Implant System and Xive).

Advantages of Acuris is quick placement of the final crown, which leads to time-saving for both the clinician and the patient, as well as a streamlined procedure. This is a fixed retention intended not to be removed unless absolutely necessary. However, the crown can easily be removed, e.g. for repair, adjustments or better access for necessary treatment, if needed. According to the Instruction For Use (IFU) the crown can be removed and reattached ten times. There is no prosthetic screw used, which might improve esthetics, due to no visible screw access holes. No cement is used for retention, and therefore there is no risk of biological complications due to excess cement.

### 1.1.1 Pre-clinical experience

Experimental studies report on different aspects of Acuris; including evaluation of the conometric mode of retention over time under dynamic loading, the retention of the conical connection between cap and abutment loaded with dynamic lateral forces after an initial axial load as well as the retention between cap and abutment, preloaded with different axial loads. These studies show that the conometric connection of the tested samples maintain its stability over time under cyclic loading, with no effect of wear detected. After dynamic lateral loading, all caps showed sufficient retention to the abutment and no cap was separated from the abutment during the tests.

### 1.1.2 Clinical experience

Conometric retention, with the use of the conic coupling abutments for fixed prostheses (fixed for the patient, removable for the clinician), has been described in a number of clinical studies including over 450 implants in over 200 patients. They cover full and partial prosthesis, placement in the mandible and maxilla, applying conventional and immediate loading protocols in extraction sockets and healed ridges, with up to 5 years of follow-up. No disconnection of any prosthesis has been reported.

The clinical use of the SynCone abutment system including Ankylos Welding Cap for SynCone 5° is also well documented. With up to 6 years of follow-up, long term reliable retention has been reported for complete overdentures when placed in the mandible, maxilla, healed sites, extraction sockets, and when applying immediate loading.

The present study is designed to obtain scientific clinical data to demonstrate long-term success of the conometric concept, Acuris, for single tooth restorations.

# 1.2 Study rationale

The clinical study is designed as a Post Market Clinical Follow-up study to provide information on clinical performance using the newly developed Acuris-conometric concept for single tooth restorations, as a new friction mode of retention for seating the abutment without using cement or screws.

The conometric abutment is developed for use with all implant brands from Dentsply Sirona

Implants (Ankylos, Astra Tech Implant System, Xive), and are used together with the conometric retention caps as retentive part of the restoration. The design for the retentive part of the abutments is similar for all implant brands to enable use of the same cap irrespective of implant system.

### 1.3 Risk/ benefit assessment

There are no obvious risks for the subjects participating in this study. There is a possibility that the new conometric retention mode might lead to technical and biological complications in a short or long-term performance. No unexpected complications beside general complications related to prosthetic restorations are being expected.

No additional x-rays compared to regular implant treatment will be taken. All attempts to limit x-ray exposure will be made during the study, including proper shielding. A benefit of taking x-rays, is the possibility to discover pathological processes at an early stage. The study subjects will benefit from careful examination and follow-up during the study participation.

# 2 Study objectives

## 2.1 Primary objective

Primary objective	Corresponding primary outcome variable
Evaluate prosthetic survival 1 year after permanent restoration	Prosthetic survival will be categorized as No/Yes.
,	It will be categorized as 'Yes' if all of the following criteria is fulfilled:
	
 
permanent restoration is remaining in situ
 
no loss of conometric retention between abutment and final cap
 
no fracture of abutment
 
no loss of abutment
 

## 2.2 Secondary objectives

Secondary objectives	Corresponding secondary outcome variables
Evaluate prosthetic survival 3 and 5 years after permanent restoration	Prosthetic survival will be categorized as No/Yes (see Primary objective)
Evaluate implant survival rate up to 5 years after permanent restoration.	Implant survival will be evaluated clinically and radiographically
Evaluate maintenance of marginal bone levels up to 5 years after permanent restoration.	Marginal Bone Levels and alterations
Evaluate condition of the peri- implant mucosa up to 5 years after permanent restoration.	Bleeding on Probing, Probing Pocket Depth and Plaque

## 2.3 Safety objectives

Safety objectives	Corresponding safety outcome variables
Evaluate Adverse Events (AE) and Adverse Device Effects (ADE)	Number and severity of AE/ADE at each study visit.

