### 5.1.5 Visit 5 Permanent Restoration (PR) (IP + max 6 months)

The permanent restoration must be in place within six months after implant placement, following the procedures described in Acuris-conometric concept Manual and product catalogd-f. Implant stability will be examined manually. A clinical examination evaluating the periimplant mucosa (Probing Pocket Depth (PPD) and Bleeding on Probing (BoP)) will be performed. Oral hygiene instruction will be given if needed. Intraoral radiographs will be obtained. Clinical photographs will be taken (at least 5 subjects). All types of safety events will be recorded.

- Remove the Conometric Temporary Crown or Conometric Healing Cap.
- Select a suitable single-use tip and attach to the Conometric Fixation Tool depending on the crown form.
- Place the final crown aligned with the index on the abutment.
- Check occlusion and contact points.
- If needed, remove the crown for correction and polishing, and then reinsert the crown aligned with the index on the abutment.
- Press the Conometric Fixation Tool towards the crown to activate the friction retention between Conometric Final Cap/final crown and abutment. An audible click occurs when the spring is released and activates the retention.
- Check retention manually.

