# 5.1.6 Visit 6-11 Follow-up (PR + 6 months, 1, 2, 3, 4, 5 years) (± 1 month)

The subject will return for follow-up visits at 6 months, 1, 2, 3, 4 and 5 years after permanent restoration. At all follow-up visits a clinical examination evaluating the presence of plaque and the condition of periimplant mucosa (PPD and BoP) will be performed. Plaque will be recorded as presence of plaque by visual inspection on four surfaces at each implant site. If a high presence of plaque is noted the subject should be re-instructed concerning oral hygiene. Intraoral radiographs will be taken at 1, 3 and 5 year follow-up visits. Clinical photographs will be taken at 1, 3 and 5 year follow-up visits (at least 5 subjects). All types of safety events will be recorded at all follow-up visits.

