# 6.4.2 AE and ADE reporting

In clinical studies, an AE can include an untoward medical condition occurring at any time, including run-in or follow-up periods, even if the subject has not been exposed to the medical device. Subjects will be observed and asked about 'any health or oral health problems since last visit' during the study. All health/oral problems, reported by the subject, found in medical records or found at the clinic visits, must be recorded in the eCRF as an AE. Information that will be collected includes:

- Event description
- Start date
- Stop date or event continuing
- Serious yes/no
- Medical device/procedure related yes/no
- Action taken due to the event
- Clinical outcome of event

If an AE is assessed to be device/procedure related it is defined as an ADE, and must be recorded in eCRF.

If an AE/ADE results in a subject's discontinuation in the study, this should be recorded at the Study Termination page in the eCRF. Not only the Investigational Product (IP), but also other medical devices used in the study, e.g. implants, conometric temporization cap and other prosthetic parts should be included in the ADE reporting.

Examples of AEs are e.g. cold, headache and abutment loss at non-study positions.

*Examples of ADEs* are e.g. implant loss, implant fracture, abutment loss, abutment fracture, screw fracture, loss of retention, at study position.

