## 10.2 Description of analysis sets

The study will be analyzed using a Safety (S) and a Per Protocol (PP) population approach. The S analysis set will consist of all enrolled subjects where any safety parameters, study specific procedures or study specific measures were performed and/or collected. Safety events will be divided and presented as two different groups depending on when the safety event started:

- 1. Pre-Permanent Restoration delivery: Safety events with start date prior to Permanent Restoration i.e. the period from Implant installation up to Permanent Restoration delivery date.
- 2. Post permanent delivery: Safety events with start date same as or after Permanent Restoration delivery i.e. Permanent Restoration delivery until end of study.

The PP analysis set will consist of all subjects fulfilling the inclusion criteria, none of the exclusion criteria and have been treated in accordance with the CIP, e.g. have an implant placed and the final permanent restoration within six months after implant placement, according to Acuris-conometric concept. Treatment efficacy related conclusions will be based on the results from the PP analysis.

All subject data will be included in subject data listings.

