### 10.3.3 Safety analysis

All safety variables will be summarized by means of descriptive statistics. No hypotheses will be tested.

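### AE/ADE counts by visit and by pre- versus post-restoration period cover unequal lengths of time; adding rates per subject-year is a cheap, minor improvement

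*Combined protocol and SAP*

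**What the plan says.** Section 2.3 gives the safety outcome as "Number and severity of AE/ADE at each study visit". Section 6.4.2 describes collection: "Subjects will be observed and asked about 'any health or oral health problems since last visit' during the study". It also lists the start date among the items recorded for each event.

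Visit 3 falls one to two weeks after implant placement (5.1.3). Visit 4 has only an upper limit of 5½ months (5.1.4). After that, "The subject will return for follow-up visits at 6 months, 1, 2, 3, 4 and 5 years after permanent restoration" (5.1.6).

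Section 10.2 adds a second display: "Safety events will be divided and presented as two different groups depending on when the safety event started". The first group is "i.e. the period from Implant installation up to Permanent Restoration delivery date". The second is described as "Safety events with start date same as or after Permanent Restoration delivery i.e. Permanent Restoration delivery until end of study". The first period is capped, because "The permanent restoration must be in place within six months after implant placement" (5.1.5). The second is a five-year follow-up from restoration (4.1).

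On method, section 10.3.3 says "All safety variables will be summarized by means of descriptive statistics" and rules out hypothesis tests. Section 10.1 defines descriptive statistics for categorical data as frequencies and percentages, and leaves a separate SAP optional. Time at risk is not used for safety anywhere in the plan.

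**The concern.** Because subjects are asked about the time since the previous visit, the number attached to a visit covers the whole interval before it. Those intervals differ widely, and so do the two periods in 10.2. Columns set side by side then differ for two reasons that a count cannot separate: how often events occur, and how long subjects were watched.

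The number at risk also changes. Loss of the study implant, or replacement of the abutment or final cap, is listed as a reason for discontinuation (5.5.1). A subject not restored within six months, or who loses the implant before restoration, leaves the study (5.5.3). Such subjects can stay in the Safety set without contributing post-restoration time.

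What is at stake is how the safety displays are read. This is a post-market study of clinical performance (1.2) with results planned at 1, 3 and 5 years (7.8, 10.5), so readers will want to know whether adverse device effects become more or less frequent over time.

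**Working it through.** **Inputs from the plan.** N = 157 (10.4). Visit timing comes from 5.1.3 to 5.1.6. The pre-restoration period is at most 6 months (5.1.5) and the post-restoration period is nominally 60 months (4.1).

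**The plan's own figure.** The plan states no expected event count or rate, so there is no safety figure to reproduce. N does reproduce: [(1.9600 × √(0.90 × 0.10) + 1.2816 × √(0.97 × 0.03)) / 0.07]² = 132.8, rounded up to 133; then 133/0.85 = 156.5, rounded up to 157. N only scales the counts below. The ratios do not depend on it.

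**Assumptions.** The event rate is constant at 0.5 per subject-year (assumed; 0.1 and 1.0 shown where useful). All 157 subjects are followed, and Visits 4 and 5 take place at their latest dates.

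**Expected count at a visit** = 157 × 0.5 × months since previous visit / 12.

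| Visit | Months since previous visit | Expected events |
|---|---|---|
| 3 | 0.23-0.46 | 1.5-3.0 |
| 4 | 5.0-5.3 | 33-35 |
| 5 | 0.5 | 3.3 |
| 6 | 6 | 39 |
| 7 | 6 | 39 |
| 8, 9, 10, 11 | 12 each | 78.5 each |

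Visit 8 to Visit 7 is 12/6 = 2.0 with no change in rate. A 12-month interval compared with the Visit 3 interval gives a ratio of 26 (two weeks) to 52 (one week).

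**Pre- versus post-restoration.**
- At 0.5 per subject-year: 157 × 0.5 × 0.5 = 39 before and 157 × 0.5 × 5 = 393 after.
- At 0.1 the totals are 8 and 79; at 1.0 they are 79 and 785.
- The ratio is 60/6 = 10 whatever the rate. It would be larger with earlier restoration (60/3 = 20 at 3 months), but the protocol gives only the maximum.

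**Drop-out (assumed exponential).** Mean post-restoration time = (1 − e^(−60h))/h.
- 15% lost over 60 months: h = −ln(0.85)/60, mean 55.4 months, ratio 55.4/6 = 9.2.
- 15% lost per year: h = −ln(0.85)/12, mean 41.1 months, ratio 6.8.

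**Percentages do not remove the effect.** The share of subjects with at least one event is 1 − e^(−rate × years). At 0.5 per subject-year this is 1 − e^(−0.25) = 22% before and 1 − e^(−2.5) = 92% after. At 0.1 it is 5% and 39%.

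**Successive reports.** With data up to the 1-, 3- and 5-year visits and restoration at 6 months, the same constant rate gives post/pre ratios of 12/6 = 2, 36/6 = 6 and 60/6 = 10.

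**With subject-time.** 39.25/(157 × 0.5) and 392.5/(157 × 5) both equal 0.5, or 50 per 100 subject-years. The ratio is 1, as it should be under no change.

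**The case against.** The strongest reply is that the plan makes no comparison for these counts to distort. Safety is descriptive, nothing is tested, there is no control arm, and no section says that visits or periods will be contrasted. The split in 10.2 has a sound purpose of its own: it sorts events by treatment phase, because the final crown is fitted only at Visit 5. The wording in 2.3 may describe the collection schedule rather than a table, and the analysis sections lay out no per-visit table. A later SAP could add rates. All of this stands, and it makes the point minor. It does not give the displays a time base, and nothing in the current text commits anyone to adding one.

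Three stronger readings are tempting, and the documents do not support them.

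- A reader might infer that early clustering or late build-up of device effects could not be recovered. It could: start and stop dates are collected (6.4.2) and all subject data go into listings (10.2). What is missing is a summary. Loss of retention and abutment fracture or loss are also part of prosthetic survival, and implant loss after restoration has its own analysis, each with an exact 95% confidence interval (6.3.1.2, 6.3.2.2, 10.3.1, 10.3.2).
- A reader might infer that all non-serious events from Visit 8 onward rest on 12 months of recall. Extra visits are allowed (5.1), and events are also taken from medical records and clinic findings (6.4.2).
- A reader might quote the extremes of the ±1 month windows, where Visit 8 to Visit 7 runs from 10/8 = 1.25 to 14/4 = 3.5. Those are limits for a single subject. The cohort ratio reaches them only if every subject sits at the same opposing limits.

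**Conclusion.** The point holds as a minor weakness in reporting. As planned, AE/ADE counts and percentages scale with the length of the interval and cannot by themselves show whether the event rate changes. Under a constant rate the built-in factor is about 2 between Visits 7 and 8. It is about 10 between the post- and pre-restoration periods for completers restored at 6 months, and about 9 with an assumed 15% drop-out over 5 years.

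These factors rest on nominal visit timing and a constant rate, which is used only as a reference. If events in fact cluster around surgery, raw counts would understate that early rate relative to later periods. The primary analysis, the sample size and the survival endpoints are unaffected.

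**What to change.** In 10.3.3, or in the SAP if one is written before database lock:

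- Keep the counts. Add events per 100 subject-years, with the number of subjects at risk, for AE and for ADE. If SAE and SADE are sparse, give only an overall rate for each.
- Report these for the pre- and post-restoration periods of 10.2 and for a few fixed post-restoration intervals, for example year 1, years 2-3 and years 4-5, which match the planned reports.
- Assign each event by its start date, and use each subject's actual time in the interval, up to termination, as the denominator.
- State that any remark about change over time, or before versus after restoration, will be based on these rates.

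The cost is a short text change and one longer table. Event start dates are already collected, the restoration date is already needed for the split in 10.2, and visit dates with the Termination section (5.5.2) supply the end of follow-up. No visit or assessment is added. The downside is that some cells will be sparse: at an assumed 0.1 events per subject-year, only about 8 events are expected before restoration (157 × 0.1 × 0.5 = 7.85).

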# 3 Ethical and legal considerations

### 3.1 Ethics review

The responsibility for submissions and communication to the Independent Ethics Committee (IEC)/Institutional Review Board (IRB) is specified in the Clinical Study Agreements (CSAs) with each participating study site according to local requirements.

The final Clinical Investigation Plan (CIP), including the final version of the Informed Consent Form (ICF), must be given a favorable opinion in writing/approval by an IEC/IRB or Regulatory Authority as appropriate before any subject can be enrolled into the study. Substantial Amendments must be submitted to the IEC/IRB and an approval must be obtained. Progress reports and notifications of Serious Adverse Events (SAEs), Serious Adverse Device Effects (SADEs) and Device Deficiencies with SADE potential will be provided to the IEC/IRB and/ or Regulatory Authorities according to local regulations and guidelines.

Dentsply Sirona Implants will provide Principal Investigators (PIs) with safety updates/reports according to local requirements.

